Eligibility Criteria

- Histologically confirmed melanoma that is recurrent/metastatic and not amenable to potentially curative surgery;
- Clinically and/or radiologically documented disease with at least one site of disease unidimensionally measurable by contrast-enhanced CT scan;
- Radiology must be performed within 28 days prior to registration (35 days if negative);
- Age \geq 18 years;
- ECOG 0 to 1;
- Previous surgery permitted as long as 21 days prior to patient registration and wound healing has occurred;
- Palliative radiation permitted as long as >7 days between last dose and enrolment on trial;
- Neutrophils $\geq 1.5 \times 10^9/L$;
- Platelets $\geq 100 \times 10^9/L$;
- Hemoglobin $\geq 90 \text{ g/L}$ or $\geq 5.6 \text{ mmol/L}$ (without transfusion or EPO dependency);
- Serum creatinine $\leq 1.5 \times \text{ULN}$ **OR** measured or calculated creatinine clearance $\geq 60 \text{ mL/min}$ for subject with creatinine levels $> 1.5 \times \text{ULN}$;
- Serum total bilirubin $\leq 1.5 \times \text{ULN}$ **OR** direct bilirubin $\leq \text{ULN}$ for subjects with total bilirubin levels $> 1.5 \times \text{ULN}$;
- AST and ALT $\leq 2.5 \times \text{ULN}$ ($\leq 5 \times \text{ULN}$ for subjects with liver mets);
- Albumin $\geq 25 \text{ g/L}$;
- Negative serum or urine pregnancy test within 7 days prior to registration (if applicable);
- Men and women of child-bearing potential must use adequate contraception as described in Section 5.1.7.

Ineligibility Criteria

- Prior systemic therapy for metastatic melanoma;
- Known history of Human Immunodeficiency Virus (HIV) (HIV 1/2 antibodies);
- Known history of or known positive for Hepatitis B (HBsAg reactive) or Hepatitis C (HCV RNA [qualitative] is detected). Patients with unknown history of HBV or HCV will require screening;
- Patients with previously treated brain metastases may participate provided they are stable with no evidence of enlargement following radiation treatment and no acute radiation toxicity **OR** no evidence of enlargement at least 4 weeks prior to the first dose of study drug if untreated and are off systemic steroids for at least two weeks;
- Patients who are pregnant or breastfeeding, or expecting to conceive or father children within the projected duration of the study;

AMEND #1: 2016-NOV-23; AMEND #2: 2017-JUL-10

- Patients who previously had a severe hypersensitivity reaction to treatment with another mAb;

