5.1.6 Laboratory Requirements (must be done within 7 days prior to registration)

Hematology:	Absolute neutrophils (ANC)	$\geq 1.5 \times 10^9/L$
	Platelets	$\geq 100 \times 10^9/L$
	Hemoglobin	$\geq 90 \text{ g/L}$ or $\geq 5.6 \text{ mmol/L}$ (without transfusion or EPO dependency)
Chemistry:	Serum creatinine	$\leq 1.5 \times \text{ULN}$
	OR	OR
	Measured or calculated creatinine clearance	$\geq 60 \text{ mL/min}$ for subject with creatinine levels $> 1.5 \times \text{ULN}$
	Serum Total Bilirubin	$\leq 1.5 \times \text{ULN}$
	OR	OR
	Direct bilirubin	$\leq \text{ULN}$ for subjects with total bilirubin levels $> 1.5 \times \text{ULN}$
	AST and ALT	$\leq 2.5 \times \text{ULN}$ ($\leq 5 \times \text{ULN}$ for subjects with liver mets)
	Albumin	$\geq 25 \text{ g/L}$

5.1.7 Women/men of childbearing potential must have agreed to use a highly effective contraceptive method. A woman is considered to be of "childbearing potential" if she has had menses at any time in the preceding 12 consecutive months. In addition to routine contraceptive methods, "effective contraception" also includes heterosexual celibacy and surgery intended to prevent pregnancy (or with a side-effect of pregnancy prevention) defined as a hysterectomy, bilateral oophorectomy or bilateral tubal ligation, or vasectomy/vasectomized partner. However, if at any point a previously celibate patient chooses to become heterosexually active during the time period for use of contraceptive measures outlined in the protocol, he/she is responsible for beginning contraceptive measures.

5.1.8 Women of childbearing potential will have a serum or urine pregnancy test within 7 days prior to registration to determine eligibility. If the urine test is positive or cannot be confirmed as negative, a serum pregnancy test will be required. This may also include an ultrasound to rule-out pregnancy if a false-positive is suspected. For example, when beta-human chorionic gonadotropin is high and partner is vasectomized, it may be associated with tumour production of hCG, as seen with some cancers. Patient will be considered eligible if an ultrasound is negative for pregnancy.

AMEND #2: 2017-JUL-10

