8.3 Dose Modification Guidelines for Drug-related Adverse Events

Toxicity	Hold Treatment For Grade	Timing for Restarting Treatment	Treatment Discontinuation
Diarrhea/Colitis	2-3	Toxicity resolves to Grade 0-1	Toxicity does not resolve within 12 weeks of last dose or inability to reduce corticosteroid to 10 mg or less of prednisone or equivalent per day within 12 weeks
	4	Permanently discontinue	Permanently discontinue
AST, ALT, or Increased Bilirubin	2	Toxicity resolves to Grade 0-1	Toxicity does not resolve within 12 weeks of last dose
	3-4	Permanently discontinue (see exception below) ^a	Permanently discontinue
Type 1 diabetes mellitus (if new onset) or Hyperglycemia	T1DM or 3-4	Hold pembrolizumab for new onset Type 1 diabetes mellitus or Grade 3-4 hyperglycemia associated with evidence of beta cell failure. Insulin replacement therapy is recommended for Type I diabetes mellitus and for grade 3-4 hyperglycemia associated with metabolic acidosis or ketonuria.	Resume pembrolizumab when patients are clinically and metabolically stable
Hypophysitis	2-4	Toxicity resolves to Grade 0-1. Therapy with pembrolizumab can be continued while endocrine replacement therapy is instituted. When symptoms improve to grade 1 or less, steroid taper should be started and continued over no less than 4 weeks.	Toxicity does not resolve within 12 weeks of last dose or inability to reduce corticosteroid to 10 mg or less of prednisone or equivalent per day within 12 weeks

table continued on next page ...

Admin Update #1: 2016-MAY-10

Toxicity	Hold Treatment For Grade	Timing for Restarting Treatment	Treatment Discontinuation
Hyperthyroidism	3	Toxicity resolves to Grade 0-1	Toxicity does not resolve within 12 weeks of last dose or inability to reduce corticosteroid to 10 mg or less of prednisone or equivalent per day within 12 weeks
	4	Permanently discontinue	Permanently discontinue
Hypothyroidism		Therapy with pembrolizumab can be continued while thyroid replacement therapy is instituted	Therapy with pembrolizumab can be continued while thyroid replacement therapy is instituted
Infusion Reaction	2 ^b	Toxicity resolves to Grade 0-1	Permanently discontinue if toxicity develops despite adequate premedication
	3-4	Permanently discontinue	Permanently discontinue

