Pneumonitis	2	Toxicity resolves to Grade 0-1. For grade 2 events treat with systemic corticosteroids. When symptoms improve to grade 1 or less, steroid taper should be started and continued over no less than 4 weeks.	Toxicity does not resolve within 12 weeks of last dose or inability to reduce corticosteroid to 10 mg or less of prednisone or equivalent per day within 12 weeks
	3-4	Permanently discontinue	Permanently discontinue
Renal Failure or Nephritis	2	Toxicity resolves to Grade 0-1	Toxicity does not resolve within 12 weeks of last dose or inability to reduce corticosteroid to 10 mg or less of prednisone or equivalent per day within 12 weeks
	3-4	Permanently discontinue	Permanently discontinue
All Other Drug-Related Toxicity	3 or Severe	Toxicity resolves to Grade 0-1	Toxicity does not resolve within 12 weeks of last dose or inability to reduce corticosteroid to 10 mg or less of prednisone or equivalent per day within 12 weeks
	4	Permanently discontinue	Permanently discontinue

Note: Permanently discontinue for any severe or Grade 3 drug-related AE that recurs or any life-threatening event.

^a For patients with liver metastasis who begin treatment with Grade 2 AST or ALT, if AST or ALT increases by greater than or equal to 50% relative to baseline and lasts for at least 1 week then patients should be discontinued.

^b If symptoms resolve within one hour of stopping drug infusion, the infusion may be restarted at 50% of the original infusion rate (e.g., from 100 mL/hr to 50 mL/hr). Otherwise dosing will be held until symptoms resolve and the subject should be premedicated for the next scheduled dose; Refer to Section 8.3.1, Infusion Related Reactions Table for further management details.

^c Patients with intolerable or persistent Grade 2 drug-related AE may hold study medication at physician discretion. Permanently discontinue study drug for persistent Grade 2 adverse reactions for which treatment with study drug has been held, that do not recover to Grade 0-1 within 12 weeks of the last dose.

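### Section 8.3: the Grade 2 hepatic hold, restart and 12-week stop ignore baseline, although the protocol admits liver-metastasis patients at Grade 2 AST/ALT and footnote a gives them a different stopping rule

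*Combined protocol and SAP*

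**What the plan says.** **Entry.** The eligibility summary and Section 5.1.6 cap AST and ALT at 2.5 x ULN, raised to 5 x ULN "for subjects with liver mets". Footnote a to Section 8.3 is written "For patients with liver metastasis who begin treatment with Grade 2 AST or ALT", so the protocol itself expects such patients.

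**Grade 2 hepatic line (Section 8.3).** Treatment is held at Grade 2. The restart condition is "Toxicity resolves to Grade 0-1" and the stopping condition is "Toxicity does not resolve within 12 weeks of last dose". This line carries no exception marker. Footnote c uses the same absolute target: a persistent Grade 2 reaction for which drug was held leads to permanent discontinuation if Grade 0-1 is not regained within 12 weeks. The point at which footnote c attaches to the table is not visible in the text as read.

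**Grade 3-4 hepatic line.** "Permanently discontinue (see exception below", with a marker to footnote a.

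**Footnote a.** It discontinues members of the liver-metastasis subgroup "who begin treatment with Grade 2 AST or ALT, if AST or ALT increases by greater than or equal to 50% relative to baseline", when the rise lasts at least one week.

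**Section 8.2.** Drug is withheld for drug-related non-hematological toxicity of Grade 3 or more, laboratory abnormalities included. Where a patient has several adverse events with conflicting advice, the most restrictive advice applies.

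**Scope.** The 8.3 table is for drug-related events, and the text after it applies the guidelines when the investigator attributes the event to pembrolizumab.

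**Bilirubin.** The same hepatic row covers it. Section 5.1.6 has a direct-bilirubin alternative "for subjects with total bilirubin levels" above 1.5 x ULN, with no ceiling on the total. Footnote a names only AST and ALT.

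**The concern.** The protocol deliberately enrols patients whose AST or ALT is already Grade 2, yet the line they are most likely to meet first, the Grade 2 line, is written as if everyone started at Grade 0-1. Only the Grade 3-4 line points to a rule expressed relative to baseline. For one drug-attributed event in one patient, the row and the footnote can therefore give different answers on whether treatment restarts or ends, and nothing says which governs.

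At stake is consistent management of an identifiable subgroup. Two sites following the same protocol could hold, resume or permanently stop identical patients.

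**Working it through.** The plan gives no figure to reproduce. The check sets the rules side by side, with one piece of arithmetic.

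**Inputs**
- Entry cap with liver metastases: 5 x ULN (eligibility summary and Section 5.1.6).
- Footnote a: rise of at least 50% over baseline B, lasting at least 1 week, so the stop level is S = 1.5 x B.
- Grade 2 line: restart at Grade 0-1; stop if unresolved 12 weeks after the last dose.
- Grade limits: Appendix V adopts CTCAE version 4.0 but the documents do not print its AST/ALT limits. Assumed here: Grade 2 ends at 5 x ULN; the floor of Grade 2 is varied over 2.5, 3.0 and 3.5 x ULN.

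**Step 1: restart and 12-week stop (no grade limits needed).** If B is Grade 2, then Grade 0-1 is by definition a lower value than B. Suppose a drug-attributed rise of less than 50% leads to a hold, and the value then returns to B.
- Grade 2 line: not resolved, so no restart, and discontinuation at 12 weeks.
- Footnote a: the rise was below 50%, so no discontinuation.

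The two instructions differ for any Grade 2 baseline.

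*Illustration.* Take B = 4.0 x ULN, rising to 4.8. The rise is 4.8/4.0 - 1 = 20%, and footnote a would act only at 1.5 x 4.0 = 6.0. To restart under the row, the value must fall to the assumed floor of Grade 2:

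| Assumed floor (x ULN) | Fall below baseline needed to restart |
|---|---|
| 2.5 | (4.0 - 2.5)/4.0 = 37.5% |
| 3.0 | (4.0 - 3.0)/4.0 = 25% |
| 3.5 | (4.0 - 3.5)/4.0 = 12.5% |

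**Step 2: rises of 50% or more that stay within Grade 2.** The stop level lies within Grade 2 when 1.5 x B is at most 5, that is, when B is at most 5/1.5 = 3.33 x ULN. Examples:
- B = 3.1: S = 4.65, still Grade 2. The row says hold; footnote a says discontinue.
- B = 3.5: S = 5.25, above the assumed ceiling.
- B = 4.0: S = 6.0.
- B = 5.0: S = 7.5, the highest stop level, at the entry cap.

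| Assumed Grade 2 floor (x ULN) | Baselines where hold and discontinue collide |
|---|---|
| 2.5 | 2.5 to 3.33 |
| 3.0 | 3.0 to 3.33 |
| 3.5 | none, since 3.5 exceeds 3.33 |

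Even inside the band, only values from 1.5 x B to 5 x ULN are affected: at B = 3.0, from 4.5 to 5.0.

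**Step 3: does Section 8.2 settle it?** Its precedence rule is worded for several adverse events. Here there is one event under two rules. Stretched to a single event, choosing the most restrictive advice would also make the Grade 3-4 stop override footnote a and so cancel the exception that the table grants.

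**The case against.** The strongest reply is that this is a narrow drafting gap. The table applies only to events attributed to pembrolizumab, and the text after it asks investigators to rule out causes such as metastatic disease. At Grade 3-4, footnote a is a labelled exception, and Section 8.2 shows that the protocol leans to the more restrictive course when advice conflicts. An investigator who knows the baseline might also read resolution sensibly.

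Most of this stands, and it excludes several stronger readings that a reader might infer:

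- *Patients are stopped for pre-existing liver values alone.* Not supported. A stable pre-dose value is not a drug-related event, so it triggers neither hold nor stop. The gap opens only after a rise is attributed to the drug.
- *Patients are dosed through Grade 3 with no hold instruction.* Not supported. Section 8.2 withholds for drug-related non-hematological toxicity of Grade 3 or more, laboratory values included, and a note to the table discontinues for a recurring Grade 3 drug-related event.
- *Rises go unrecognised.* Not supported. Section 9.1 requires AST, ALT and bilirubin on Day 1 of each cycle, drawn within 72 hours before treatment.
- *The Grade 3-4 line contradicts footnote a.* Not supported. It is a rule with a marked exception.

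What the reply does not remove is the Grade 2 line. It states an absolute target, footnote c repeats that target, and neither mentions baseline. A sensible reading by one investigator does not make the written rule uniform across centres.

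**Conclusion.** The point holds in this form: the Grade 2 hold, restart and 12-week stop are not adapted to a Grade 2 baseline, and footnote a is attached only to the Grade 3-4 line, with no stated precedence.

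The restart and 12-week conflict rests on the text alone and applies to every Grade 2 starter who is held for a drug-attributed rise below 50% and does not fall below baseline into Grade 0-1. The hold-versus-discontinue conflict is smaller and depends on unprinted grade limits: baselines of 2.5-3.33, 3.0-3.33 or none, with Grade 2 assumed to end at 5 x ULN.

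The documents do not say how many of the 84 planned patients would start at Grade 2, so the frequency is unknown. A reader might infer from Section 10.2.5, which counts best response only up to the end of treatment, that avoidable stops would add non-responders and distort the texture comparison. Nothing in the documents quantifies that, and it is not claimed here. The sample size is unaffected. It should be corrected because it bears on the management of patients whom the protocol chooses to enrol.

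**What to change.** Reconcile Section 5.1.6, the withholding statement in Section 8.2, both lines of the hepatic row in Section 8.3, and footnotes a and c. The amended text should state:

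1. which single instruction governs patients who start at Grade 2 AST/ALT, for values that stay within Grade 2 and for values that reach Grade 3-4;
2. whether restart and the 12-week limit refer to absolute grade or to the patient's baseline;
3. how the Section 8.2 hold at Grade 3 or above fits with footnote a, which gives only a stopping criterion.

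At the same time, check how the row applies to a drug-attributed rise in total bilirubin in patients admitted under the direct-bilirubin clause. The clinical lead sets the rule and any thresholds; none is proposed here.

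The cost is amendment wording for one table row, its footnotes and the matching sentence in Section 8.2. No new data are needed, because baseline AST, ALT and bilirubin are already collected under Section 6.0.

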8.3.1 Infusion Related Reactions

NCI CTCAE Grade	Treatment	Premedication at subsequent dosing
Grade 1 Mild reaction; infusion interruption not indicated; intervention not indicated	Increase monitoring of vital signs as medically indicated until the subject is deemed medically stable in the opinion of the investigator.	None
Grade 2 Requires infusion interruption but responds promptly to symptomatic treatment (e.g. antihistamines, NSAIDS, narcotics, IV fluids); prophylactic medications indicated for \leq 24 hrs	
Stop Infusion and monitor symptoms.
 
Additional appropriate medical therapy may include but is not limited to:
 
 – IV fluids – Antihistamines – NSAIDS – Acetaminophen – Narcotics 
Increase monitoring of vital signs as medically indicated until the subject is deemed medically stable in the opinion of the investigator.
 
If symptoms resolve within one hour of stopping drug infusion, the infusion may be restarted at 50% of the original infusion rate (e.g. from 100 mL/hr to 50 mL/hr). Otherwise dosing will be held until symptoms resolve and the subject should be premedicated for the next scheduled dose.
 
Subjects who develop Grade 2 toxicity despite adequate premedication should be permanently discontinued from further trial treatment administration.
	
Subject may be premedicated 1.5h (\pm 30 minutes) prior to infusion of pembrolizumab (MK-3475) with:
 
Diphenhydramine 50 mg po (or equivalent dose of antihistamine).
 
Acetaminophen 500-1000 mg po (or equivalent dose of antipyretic).

Grades 3 or 4 Grade 3: Prolonged (i.e., not rapidly responsive to symptomatic medication and/or brief interruption of infusion); recurrence of symptoms following initial improvement; hospitalization indicated for other clinical sequelae (e.g., renal impairment, pulmonary infiltrates) Grade 4: Life-threatening; pressor or ventilatory support indicated	
Stop Infusion.
 
Additional appropriate medical therapy may include but is not limited to:
 
 – IV fluids – Antihistamines – NSAIDS – Acetaminophen – Narcotics – Oxygen – Pressors – Corticosteroids – Epinephrine 
Increase monitoring of vital signs as medically indicated until the subject is deemed medically stable in the opinion of the investigator.
 
Hospitalization may be indicated.
 
Subject is permanently discontinued from further trial treatment administration.
	No subsequent dosing

Appropriate resuscitation equipment should be available in the room and a physician readily available during the period of drug administration.

8.4 Duration of Protocol Treatment

Treatment will continue until the criteria for removal from protocol treatment have been met (see Section 12.0).

8.5 Concomitant Therapy

8.5.1 Permitted

Patients may receive ongoing supportive and palliative care (e.g. pain control) as clinically indicated throughout the study. Physiological doses of systemic corticosteroids are allowed, as well as inhaled, topical and prophylaxis use for allergic reactions, such as IV contrast dye. All supportive medications must be recorded on the electronic case report form as appropriate.

8.5.2 Not Permitted

- Antineoplastic systemic chemotherapy or biological therapy.
- Immunotherapy including corticosteroids (see Section 8.5.1), except for treatment of potential immune-related AEs during the study.
- Investigational agents other than pembrolizumab.
- Radiation therapy (Note: radiation therapy to a symptomatic solitary lesion may be allowed after consultation with CCTG). Radiation to target lesions should be avoided and if required, patient would be considered to have progressive disease.
- Live vaccines within 30 days prior to the first dose of study therapy and while on study. Examples of live vaccines include, but are not limited to, the following: measles, mumps, rubella, chicken pox, yellow fever, seasonal flu, H1N1 flu, rabies, BCG, and typhoid vaccine.

9.0 EVALUATION DURING AND AFTER PROTOCOL TREATMENT

All patients entered on study must be evaluated according to the schedule outlined in Appendix I with documentation submitted according to the schedule in Appendix IV.

9.1 Evaluation During Protocol Treatment

	Investigations	Timing
History and Physical Exam including:	
 history weight ECOG Performance status vital signs (blood pressure and pulse) clinical tumour measurements (if applicable) 	Day 1 each cycle
Hematology*	
 CBC, differential, platelets 	Day 1 each cycle
Biochemistry*	
 electrolytes (sodium, potassium, chloride, bicarbonate) alkaline phosphatase AST, ALT serum creatinine bilirubin 	Day 1 each cycle
	
 phosphorous calcium magnesium albumin 	As clinically indicated
	
 TSH, FT3, FT4 	Every other cycle
Radiology**	
 CT scan with contrast of chest, abdomen/pelvis Other sites as clinically indicated 	4 weeks, 12 weeks, then every 12 weeks
Other Investigations	
 ECG 	As clinically indicated
Economics	
 Health Utilities Index (EQ-5D) Resource Utilization Assessment 	To be completed at each 12 weekly visit until progression OR maximum 1 year from registration
Adverse Events***	Patients must be evaluated after each cycle for adverse events	

* Bloodwork Timing: Pre-treatment blood draws should be done within 72 hours (maximum) prior to treatment.

** Patients with a CR or PR should have scans repeated after minimum 4 weeks to confirm response. See Appendix VII for CT requirements.

*** Adverse events will be recorded and graded according to the NCI Common Terminology Criteria for Adverse Events (CTCAE) (Appendix V).

9.2 Evaluation After Protocol Treatment

All patients will be seen at 4 weeks after the end of the last cycle date. Thereafter, continued follow-up is not required for patients who go off protocol treatment with progressive disease, except to document ongoing toxicities (until resolved to \leq grade 2) and late toxicities (including second malignancies). Patients who go off protocol therapy before progression is documented or have objective CR, PR or SD ongoing, follow-up and a Follow-up Report will be required at least every 3 months for a maximum of 1 year, (See Appendix I for investigations to be performed). Death Report will be required for all patients. Due within 2 weeks of knowledge of death (see Appendix IV - Documentation for Study).

Investigations		Timing
History and Physical Exam including:	
 history weight ECOG Performance status vital signs (blood pressure and pulse) clinical tumour measurements (if applicable) 	4 weeks post end of last cycle
Hematology	
 CBC, differential, platelets 	4 weeks post end of last cycle
Biochemistry	
 electrolytes (sodium, potassium, chloride, bicarbonate) alkaline phosphatase AST, ALT serum creatinine bilirubin 	4 weeks post end of last cycle
	
 phosphorous calcium magnesium albumin 	As clinically indicated
Radiology*	
 CT with contrast of chest, abdomen and pelvis 	As per standard of care (at least every 3 months) until progression or a maximum of 1 year
Other Investigations	
 ECG 	As clinically indicated
Adverse Events	Adverse events will be recorded and graded according to the NCI Common Terminology Criteria for Adverse Events (CTCAE) (Appendix V).	4 weeks post end of last cycle
* Patients with a CR or PR should have scans repeated after minimum 4 weeks to confirm response.		

AMEND #1: 2016-NOV-23

